Five patients will be enrolled into each stratum for evaluation of graft augmentation. If none of the five patients per stratum show any graft augmentation after one year, accrual to that particular stratum will be closed due to lack of efficacy. Patients will continue to be enrolled into other strata until criteria for five patients per stratum are fulfilled. If one out of five patients per stratum will meet listed criteria for graft augmentation, the next five patients may be enrolled to that stratum. If graft augmentation is seen in 1 of 5 or 2 of 10 cases in any stratum the strategy will be considered worthy of further investigation.

Since initiation of the study, it has been noted that stratum III encompasses a wide variety of diseases and therefore the majority of subjects enrolled have been to this stratum. As at least one subject has met the criteria for improved graft augmentation, the target enrollment for stratum III will be increased to 15 to accommodate this large group of patients.

If the infusion of purified CD34+ donor cells does not increase graft augmentation, patient will be removed from study and treated according to standard procedures.

There are no specific plans at this time to treat the patient with an additional boost of CD34+ cells if graft augmentation does not occur on study. However, this decision will be made on a per case basis as clinically indicated.

2a. Inclusion Criteria

To be eligible for this protocol, patients must have the following:

- 1. Primary immunodeficiency (e.g. SCID, Wiskott-Aldrich and/or other more rare conditions), or a bone marrow failure syndrome with prior allogeneic stem cell transplant.
- 2. Waning donor chimerism or immune function that is inadequate to correct their disease or clinical condition, for which primary transplant was given, as determined by their attending physician.
- 3. Available primary donor.
- 4. Must not have other organ dysfunction deemed by the attending physician to preclude this procedure.

- 5. Age < 35 years at time of transplant
- 6. One of the following must be true:
 - Patients must have evidence of persistent or recurrent immunodeficiency or thrombocytopenia.

-OR-

• Primary immunodeficiency disease with known potential to progress to malignant condition if untreated.

-OR-

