No additional immune suppression will be given after stem cell infusion. The stem cell product will be highly T-cell depleted, reducing risk of GVHD. In addition the patient is already a mixed chimera (has both donor and own cells) and likely tolerant of donor cells. Occurrence of GVHD in these settings is unlikely.

Support therapy:

• Any infusion related reactions will be treated with supportive therapy.

- Patients with fever (temperature of 38.0°C or above) will be treated in compliance with institution guidelines in regards to disease risk and immune status of the patient.
- Blood products may be administered according to standard of care and institutional guidelines for immunodeficient patients if needed for medical condition or prophylaxis.
- Patients may remain on current medication that they are taking for their medical problems or infection prophylaxis as per attending physician decision.
- If acute or chronic GVHD occurs, patients will be treated according to standard of care.

Stem Cell Processing:

The CD34+ cells will be separated by CliniMACs cell purification protocols which are not yet licensed in the US. This protocol will be submitted to the FDA under an existing IND.

Peripheral blood stem cells (PBSC) with a target of $\geq 10 \times 10^6$ /kg CD34+ cells will be requested. All CD34+ stem cells will be infused if more than 10×10^6 /kg CD34+ stem cells are collected. The maximum number of CD34+ cells that will be infused will be defined by the maximum T-cell (CD3+) dose. Stem cells will be depleted of T-cells using a CliniMACS CD34+ cell selection device and infused into the patient with a maximum Tcell dose of 5 x 10⁴/kg. The minimum number of CD34+ cells that will be infused is 1×10^6 /kg. Stem cell processing will occur at Hoxworth Blood Center per standard operating procedures. If T-cell depletion yields a product that does not meet the release parameters, the product will not be infused, although a portion of the product may be given if the T cell content of the entire product exceeds the specified maximum dose. (See the table below.) As the patient has not received a preparative regimen, there will be no negative consequences.

Product Release Parameters

Attribute	Test Method	Specification
Volume	Measured	≤ 20 mL/kg
Total Cell Count	Hemacytometer	Report Value
Viability	7AAD	≥ 80%
% CD34+	Flow Cytometry	≥ 70%
Viable CD34+/Kg	Flow Cytometry	≥ 10 ⁶ /kg
% CD3+	Flow Cytometry	Report Value

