Appropriate immunologic studies relevant to indications for CD34 infusion will be performed for stratum II and stratum III patients (see strata on page 6) at three months (+/- four weeks) and at or around six, twelve months and annually for up to 3 years post infusion. These tests will include, but not be limited to, lymphocyte subsets, T cell activation and NK function.

Additional testing like disease specific markers (CD132, WASP) or more frequent testing might be needed at attending physician discretion if indicated by patient's clinical condition.

5. Blood Specimens

Not applicable

6. Other Previously Approved Research Studies In Which The Projected Patient Population May Also Be Involved (include what precautions will be taken to avoid any cumulative risk, e.g., repeated blood sampling, radiation exposure, etc.)

Patients eligible for this study may beeligible for other open therapeutic studies at CCHMC. Study options will be discussed and decided on a case-by-case basis.

7. Data Analysis/Statistical Considerations

Primary Endpoints

The primary endpoint of the study is augmentation of graft function. Graft function will be measured in two ways: firstly the percentage of donor chimerism, and secondly immune function.

Successful augmentation of graft function will be achieved if:

- Donor chimerism is doubled compared to the value immediately pre-infusion at 3, 6, and 12 months, -OR-
- Improvement in immune function studies compared to baseline levels can be documented at 3, 6, and 12 months. Example of immune function studies which would be used would include quantitation of T and B cells and functional studies (mitogens and Immunoglobulin levels). In the case of Wiskott-Aldrich syndrome, improvement of platelet count to >20,000/L without transfusions on 2 separate occasions at least three months apart will be considered successful graft augmentation. Children requiring graft augmentation for a specific limited immune defect, e.g. inability to clear papilloma virus will also be assessed by

clinical response of the infection; resolution or >50% improvement in infection will be considered successful graft augmentation.

Secondary Endpoints

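### Outside the Wiskott-Aldrich platelet criterion, the primary endpoint has no rule to stop co-treatment, chiefly immunoglobulin replacement, from being scored as graft augmentation

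*Combined protocol and SAP*

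**What the plan says.** **Endpoint.** Section IV.7 (Primary Endpoints) makes either of two limbs sufficient. The first is "Donor chimerism is doubled compared to the value immediately pre-infusion at 3, 6, and 12 months, -OR". The second is "Improvement in immune function studies compared to baseline levels can be documented at 3, 6, and 12 months", with T- and B-cell counts and "functional studies (mitogens and Immunoglobulin levels" as examples. No size of improvement is set. For children treated because of a circumscribed immune defect, such as failure to clear papilloma virus, "resolution or >50% improvement in infection will be considered successful graft augmentation". That criterion has no time point.

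**Existing guard.** In IV.7 the Wiskott-Aldrich platelet criterion requires the counts to be reached without transfusion. Section I (Endpoints) gives the same criterion without that condition. It also lists better white-cell or platelet numbers and viral clearance as measures of graft function, again with no co-treatment condition.

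**Permitted co-treatment.** Under Procedures, Support therapy: "Blood products may be administered according to standard of care and institutional guidelines for immunodeficient patients if needed for medical condition or prophylaxis". Also: "Patients may remain on current medication that they are taking for their medical problems or infection prophylaxis as per attending physician decision".

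**Decision rule.** The enrolment text before 2a closes a stratum at 0 of 5 responders and allows five more patients at 1 of 5. It treats 1 of 5 or 2 of 10 as enough to pursue the strategy further. Stopping Rules in IV.7 repeats the 0-of-5 and 1-of-5 steps. Randomization is marked not applicable, and each patient is compared with his or her own baseline.

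**The concern.** In a single-arm trial scored against baseline, the wording of the endpoint is the main protection against crediting the infusion with the effect of something else. The authors saw this for platelets and wrote a guard. The same reasoning applies to an immunoglobulin level, which replacement therapy can raise directly, and to an infection, which another treatment may clear. Neither has a guard.

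The exposure is not spread evenly. Required Observations limits chimerism testing to patients infused for inadequate chimerism. Everyone else can succeed only through the immune-function and infection criteria.

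The stratum result is at stake. Because the rule turns on a single responder, one misattributed response can keep open a stratum that would otherwise close, or label the approach worth pursuing there.

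**Working it through.** **1. Criteria and guards side by side**

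| Criterion | Co-treatment that could move it | Guard in IV.7 | Guard in section I |
|---|---|---|---|
| Wiskott-Aldrich platelets | Platelet transfusion | Yes | No |
| Immunoglobulin level | Immunoglobulin replacement (inferred from blood products) | No | No |
| T- and B-cell counts, mitogens | Not directly supplied by infused immunoglobulin | No | No |
| Infection response | Newly started anti-infective or investigational therapy | No | No |

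The gap that matters is in the second and fourth rows, together with the mismatch in the first.

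**2. Effect on the stratum decision**

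The plan states no null response rate, alpha or power, so there is no figure to reproduce. Let p be the share of patients who would be scored as responders only because of co-treatment, with an inactive infusion and no other source of response. The documents give no value for p. I assume 5%, 10% and 20%.

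*Reading A: at least 1 of 5 is a pass.* P = 1 − (1 − p)^5

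- p = 0.05: 1 − 0.95^5 = 0.226
- p = 0.10: 1 − 0.90^5 = 0.410
- p = 0.20: 1 − 0.80^5 = 0.672

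*Reading B: at least 1 of the first 5, then at least 2 of 10 overall.* P = P(X1 = 1) × P(X2 ≥ 1) + P(X1 ≥ 2), where X1 and X2 are the responders in the first and second five.

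- p = 0.05: 0.2036 × 0.2262 + 0.0226 = 0.069
- p = 0.10: 0.3281 × 0.4095 + 0.0815 = 0.216
- p = 0.20: 0.4096 × 0.6723 + 0.2627 = 0.538

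With p = 0, both readings give 0. The text supports either reading, so both belong in the result. Stratum III was enlarged to 15, but the available text gives no response threshold for 15, so I have not extended the calculation to it.

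**The case against.** Several points on the other side have force.

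- **Immunoglobulin is inferred.** Support therapy says blood products. IV.7 speaks of immune function studies in the plural and does not say that one immunoglobulin rise is enough. The follow-up tests named under Required Observations are lymphocyte subsets, T-cell activation and NK function. A patient on stable replacement at baseline may show no rise. If success is needed at all three visits, replacement would have to start before month 3. This narrows the route. It does not close it, because immunoglobulin levels are a named measure and no rule says how replacement is handled.
- **Anti-infectives.** The medication sentence covers treatment already in use. One entry route also requires disease that other medical treatment could not control. But that is one of three alternatives, and it is silent on therapy started after infusion. The infection criterion has no time point to limit it.
- **A later boost or chimerism.** A reader might infer that a second CD34+ infusion at, say, month 4 could produce a scored chimerism response at month 12. The documents do not support this as a plain reading. No boost is planned. It is raised only after augmentation fails ("However, this decision will be made on a per case basis as clinically indicated"), and such patients leave the study. If doubling is needed at months 3, 6 and 12, failure at month 3 is already final.
- **Co-enrolment.** A reader might take the statement that patients may be eligible "for other open therapeutic studies at CCHMC" as plain permission for concurrent treatment. The section heading points that way, but the text can also mean choosing between studies.
- **Consequence.** Passing a stratum justifies only further study. It would be too strong to say that one such response reverses the efficacy conclusion of the trial.

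**Conclusion.** The concern stands in a limited form. IV.7 protects one criterion against co-treatment and leaves the immunoglobulin-level and infection criteria unprotected. Section I drops even the platelet protection. In an uncontrolled design where one responder in five keeps a stratum open, one response produced by co-treatment can change that stratum's result.

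On assumed rates of 5% to 20%, an inactive infusion passes a stratum 23% to 67% of the time under the looser reading and 7% to 54% under the stricter one. These figures show how sensitive the rule is. They are not evidence that such responses occurred or how common they would be.

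The conclusion rests on reading blood products to include immunoglobulin replacement, and on no co-treatment rule appearing in the pages that were not available, which include the strata definitions. Confidence is therefore moderate. The sponsor should act on it, because the remedy is specific and cheap.

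**What to change.** These changes affect scoring and reporting only. Patient care is unchanged.

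1. In IV.7, count an immunoglobulin level towards response only if the follow-up sample is taken off immunoglobulin replacement, and define what off means for this purpose. Otherwise judge that patient on the T- and B-cell counts and mitogen results already listed, and keep the patient in the denominator. The condition should apply to the follow-up sample only. Requiring it at baseline too would discard the result of a patient who comes off replacement and sustains the level, which is good evidence of graft function.
2. Carry the transfusion-free condition into the platelet criterion in section I, so that sections I and IV.7 agree.
3. Record the dates of immunoglobulin replacement, newly started anti-infective or investigational therapy, and any further donor-cell product. Report responses by limb. Report each stratum's responder count with and without infection responses that followed such newly started therapy. Whether such a response is due to the graft is a matter of judgement, so showing both counts is better than scoring all of them as failures.

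The cost is revised endpoint wording and a short case report form page. The responder count may be lower.

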The purpose of this study is to investigate the usefulness of infusing purified CD34+ cells of donor origin in order to augment graft function in response to declining chimerism after initially performing an allogeneic hematopoietic stem cell transplant (HSCT) for children with primary immunodeficiency diseases. This protocol will be utilized for patients with waning mixed donor chimerism that is inadequate for correction of clinical condition or disease for which stem cell transplant was performed, or for augmentation of immune function. An infusion of selected CD34+ stem cells will be given without any preparative regimen. As the children eligible for this protocol have reduced immune function and pre-existing donor chimerism, we hypothesize that stem cells will be able to engraft and the infusion will augment graft function. This therapy serves as an alternative to a second stem cell transplant that is known to be associated with significant morbidity and mortality. CD34+ stem cells will be collected from the donor used for initial stem cell transplant. Cells will be T-cell depleted (TCD) by performing a CD34 selection using the CliniMACS device (Miltenyi Biotec) in order to prevent development of new or exacerbation of existing graft versus host disease (GVHD), as avoidance of GVHD in nonmalignant diseases is desirable. There is sufficient data showing that mixed donor chimerism is adequate for reverting disease phenotype in certain primary immunodeficiencies. Observations from Europe and CCHMC show that donor chimerism might be boosted by CD34+ stem cell infusion alone without any specific preparative regimen. This therapy is likely to be associated with low toxicity due to the absence of a preparative regimen and lack of exposure to fresh donor cells capable of initiating GVHD, and offers potential significant benefit.

I. PURPOSE OF STUDY

Hypothesis

Mixed or full donor chimerism that is adequate for disease control will be achieved with selected CD34+ stem cell infusion without preparative regimen with minimal or no therapy related toxicity or GVHD.

Objectives

- 1. Assess the toxicity of infusion of donor stem cells in augmentation of graft function in previously transplanted children with immune deficiencies, and bone marrow failures.
- Assess the efficacy of infusion of donor stem cells in augmentation of graft function in previously transplanted children with immune deficiencies, and bone marrow failures.

Endpoints

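### Sections I and IV.7 disagree on whether blood-count recovery is graft augmentation, and neither gives a measurable count response for bone marrow failure or for thrombocytopenia outside Wiskott-Aldrich syndrome

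*Combined protocol and SAP*

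**What the plan says.** **Who is studied.** Inclusion criterion 1 admits patients with a primary immunodeficiency "or a bone marrow failure syndrome with prior allogeneic stem cell transplant". Both objectives in Section I, toxicity and efficacy, are set "in previously transplanted children with immune deficiencies, and bone marrow failures". Criterion 6 offers three alternatives, of which the first reads "Patients must have evidence of persistent or recurrent immunodeficiency or thrombocytopenia" and is not tied to a diagnosis.

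**How success is defined in Section IV.7 (Primary Endpoints).** "Graft function will be measured in two ways: firstly the percentage of donor chimerism, and secondly immune function". The criteria that follow are:
- for any diagnosis, "Donor chimerism is doubled compared to the value immediately pre-infusion at 3, 6, and 12 months";
- or, for any diagnosis, "Improvement in immune function studies compared to baseline levels can be documented at 3, 6, and 12 months";
- for one disease, the platelet rule: "In the case of Wiskott-Aldrich syndrome, improvement of platelet count to >20,000/L without transfusions on 2 separate occasions at least three months apart";
- for a specific limited immune defect, resolution of the infection or more than 50% improvement.

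**How the same endpoint is put in Section I (Endpoints).** The second measure of graft function there also takes in rising white cell or platelet numbers and clearance of opportunistic viral infection, with no restriction by diagnosis. The only platelet rule with a threshold is again for Wiskott-Aldrich syndrome, and in Section I it lacks the transfusion condition found in IV.7.

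**What is done with the result.** A stratum with no response in its first five patients is closed for lack of efficacy. One response in five, or two in ten, marks the strategy as worth pursuing.

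**The concern.** For some patients with bone marrow failure, and for some others entered for thrombocytopenia, the blood count is the reason for the infusion. The Potential Benefits section presents corrected thrombocytopenia and freedom from platelet transfusion as hoped-for results, and does not confine them to Wiskott-Aldrich syndrome. IV.7 credits that result in one disease only.

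An assessor using Section I could call a platelet recovery in bone marrow failure a success. An assessor using IV.7 could not, unless another criterion was also met. With five patients per stratum, one such call can decide whether a stratum closes. It also decides who is placed among responders in the planned description of responding and non-responding cases. The efficacy objective would then be answered for bone marrow failure by measures that may not reflect why the patient was treated.

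**Working it through.** **Step 1. The two endpoint statements side by side.**

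| Outcome | Section I | Section IV.7 |
|---|---|---|
| Donor chimerism | Named as a measure, no threshold | Doubled at 3, 6 and 12 months |
| Immune function studies | Improved at 3, 6 and 12 months | Improved at 3, 6 and 12 months |
| Platelets, Wiskott-Aldrich | Threshold, two occasions | Threshold, two occasions, transfusion-free |
| Platelets, any other diagnosis | Named, no threshold or timing | Absent |
| White cells | Named, no threshold or timing | Absent, apart from T and B cell numbers as an example of immune studies |
| Red cells or hemoglobin | Absent | Absent |

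The sections disagree on platelets and white cells outside Wiskott-Aldrich syndrome. Neither has a measurable rule for them.

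**Step 2. Can the other IV.7 routes pick these patients up?** Not reliably.
- Chimerism: for a baseline of b%, doubling requires 2b ≤ 100, so b ≤ 50. A patient above 50% donor cannot meet it. Required Observations also limits post-infusion chimerism testing to patients infused because chimerism was inadequate.
- Immune function: Required Observations asks for these studies in strata II and III only.
- Infection response: applies only to a specific limited immune defect.

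**Step 3. Effect on the five-patient rule.** The plan states no response rate, alpha or power, so it has no figure to reproduce, and the target accrual of 45 does not enter. All rates here are assumptions. Let p be the true response rate in a stratum and m the share of true responders who recover counts only. Under IV.7 the scored rate is q = p(1 − m), and with independent patients P(0 of 5) = (1 − q)^5.

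| p | m = 0 | m = 0.25 | m = 0.5 |
|---|---|---|---|
| 30% | 0.70^5 = 16.8% | 0.775^5 = 28.0% | 0.85^5 = 44.4% |
| 40% | 0.60^5 = 7.8% | 0.70^5 = 16.8% | 0.80^5 = 32.8% |
| 50% | 0.50^5 = 3.1% | 0.625^5 = 9.5% | 0.75^5 = 23.7% |

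**Step 4. Effect on the ten-patient rule.** Taken on its own, the chance of at least two responses in ten is 95.4% at a scored rate of 40% and 62.4% at 20% (p = 40%, m = 0.5).

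**The case against.** The strongest reply has four parts.

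1. Section I already counts white cells and platelets, and IV.7 gives its immune studies only as examples and places Wiskott-Aldrich platelets and infection response under the same bullet. On this view the intent is broad and the wording merely short. This stands to the extent that the documents as a whole do not score count recovery as failure; they conflict. Restoring the Section I clause to IV.7 would bring in platelets and white cells, but still without threshold, timing or transfusion rule, and without red cells. The general immune-function route also lacks a threshold, but that does not supply a count rule.

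2. Inclusion criterion 2 requires waning chimerism or inadequate immune function in every entrant, so many will have one of the two general routes open. This also stands, and it narrows the group affected. It does not empty it: chimerism can be judged inadequate at a level too high to double.

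3. The strata definitions are not in the text available, so it cannot be checked where bone marrow failure patients sit or whether a count response is defined there. This stands and limits any statement about closure.

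4. In stratum III, which took most of the enrolment, at least one patient has already met the criteria. Closure at 0 of 5 is therefore not the risk there; an understated response count is.

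A reader might go further and infer that bone marrow failure patients usually enter through thrombocytopenia. Criterion 6 gives immunodeficiency and thrombocytopenia as alternatives, and nothing in the text says how often each applies.

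**Conclusion.** The point holds in a limited form. The two endpoint statements conflict on blood counts, and the visible text contains no measurable count response for bone marrow failure, a population named in the efficacy objective, or for patients outside Wiskott-Aldrich syndrome entered for thrombocytopenia. Applied as written, IV.7 makes a count-only responder a non-responder in the stratum rules.

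Two stronger readings are not supported. One is that count recovery in bone marrow failure is always scored as failure: Section I points the other way, and such a patient can still succeed through another route. The other is that a stratum of these patients would certainly close: that requires five count-only patients in one stratum, and no such composition appears in the documents.

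The size is therefore illustrative. If half of true responders recover counts only, the chance of no scored response in five rises by about 21 to 28 percentage points over assumed true rates of 30% to 50%; if a quarter do, by about 6 to 11 points. These figures assume independent patients, scoring by IV.7 alone, and a stratum in which such patients occur.

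**What to change.** - Reconcile Sections I and IV.7 so that one statement of the primary endpoint governs, including whether the Wiskott-Aldrich platelet rule requires freedom from transfusion.
- Record at enrolment the indication for the infusion (chimerism, immune function, cytopenia by lineage, or infection), so that the applicable criterion is fixed before the outcome is known.
- Add to IV.7 a count response, defined by the sponsor, for bone marrow failure and for every patient entered for thrombocytopenia. It should state lineage (including red cells where relevant), threshold, timing and transfusion independence.
- Do not carry the 20,000/L platelet figure across unchecked. Its unit and its suitability for other diagnoses need the sponsor's confirmation.
- State whether patients already enrolled will be re-scored under the amended definition, and report results under both.

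The cost is small: endpoint wording, plus case report form fields for indication and transfusion dates. CBCs are already required at 3, 6 and 12 months. Transfusion dates are not listed in Required Observations and a CBC does not supply them, so that field is a real addition.
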